10.2 Hypothesis

Null hypothesis: perioperative treatment of patients undergoing bariatric surgery with lidocaine has no impact on postoperative quality of analgesia.

Alternative hypothesis: perioperative treatment of patients undergoing bariatric surgery with lidocaine reduces the proportion of patients suffering from more intensive pain (any development of VAS/NRS score > 3 , in hourly measurements) within the first four hours from currently 65% to 35%.

10.3 Determination of Sample Size

With an expected postoperative VAS/NRS score (any development during first four hours after completion of surgery) of > 3 points in patients undergoing elective bariatric surgery of 65% in the control group, the expected frequency of VAS/NRS score ≤ 3 is 65% in the interventional group. A two group test with a 0.05 two-sided significance level will have 90% power to detect a redistribution of VAS/NRS score ≤ 3 points in favour of interventional group when the sample size in each group is 63. Assuming a 10% dropout rate, 140 subjects will be recruited and randomized. Sample size was calculated according to Jaykaran et al. with a sample size calculation for χ^2 tests using web-based sample size calculator on biomath.info. (55, 56)

10.4 Planned Analyses

Following populations will be analyzed

- Interventional group (patients receiving lidocaine 1% I.V. in addition to general anesthesia)
- Control group (patients receiving saline 0.9% as placebo I.V. in addition to general anesthesia)
- whole population (evaluation of secondary endpoints)

10.5 Primary and secondary endpoint analyses

Potential differences between the two groups in the distribution of dichotomous data will be analysed by χ^2 statistics. Continuous data will be analyzed by parametric or non-parametric test for unpaired comparison as appropriate. Statistics will be calculated with SPSS. We will consider the null hypothesis refuted if p-value is < 0.05 .

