6. STUDY DESIGN

6.1 General study design and justification of design

The study design will be randomized, double blinded and placebo controlled. All patients complying our inclusion criteria will be included to the selection procedure. Patients will be informed about the study sequence during preoperative anesthesiological consultation to give their informed consent. Patients` data will be subsequently integrated to the eCRF. Each participant will be linked with a unique identification code which will be used for continuing process. Furthermore, information about sex, date of birth, date of surgery, indication, BMI, ASA classification, medical history and allergies will be recorded. Patients denying informed consent will be excluded from the pool of selected patients.

The intervention to be studied will either be the additional application of systemic lidocaine 1% dosed 1.5 ml/kg LBM to general anesthesia in bariatric surgery or the application of placebo. Patients, randomly assigned to one study group, will be surveyed for 48 hours after completion of surgery, experienced pain, occurrence of PONV, time to first defecation and length of hospitalization will be monitored. The population to be studied will include 140 patients listed for bariatric surgery at the Kantonsspital St. Gallen and fulfilling criteria for inclusion, respectively without criteria for exclusion. Patients, medical practitioner, nurses and investigators will be blinded by utilization of equal appearance and packing of IMPs, which will be fabricated individually for each patient and on request one to two days before surgery by the pharmacy of the Kantonsspital St. Gallen. Each patient will self-evaluate his maximal experienced pain eight-hourly during a sequence of 48 hours after completion of surgery. Study observation ends with study nurses` final visit on second postoperative day 2pm respectively +/- 30 minutes.

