6.3 Randomization

Patients selected to participate will be randomized automatically after giving their informed consent using a computerized block randomization process (10 patients per block). Patients will be randomized 1:1 to either “lidocaine group” or “placebo group”.

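### All planned comparisons are unadjusted although sex, age, BMI and ASA class are recorded before surgery: a modest missed efficiency, not an error

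*Combined protocol and SAP*

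**What the plan says.** Section 10.5 (Primary and secondary endpoint analyses) states: "Potential differences between the two groups in the distribution of dichotomous data will be analysed by" χ² statistics. Continuous data get a parametric or non-parametric unpaired test. No section names a covariate, a regression model, a stratified test or an adjusted sensitivity analysis.

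Section 6.3 (Randomization) allocates "using a computerized block randomization process (10 patients per block"), and adds: "Patients will be randomized 1:1 to either “lidocaine group” or “placebo group". Section 7.4 repeats this. Neither names a stratification factor.

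Section 6.1 lists what is entered for each participant: "Furthermore, information about sex, date of birth, date of surgery, indication, BMI, ASA classification, medical history and allergies will be recorded". Section 7.3 places recruitment at the preoperative consultation, two to three weeks before admission. No baseline pain score is listed.

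Section 9.2 also expresses ward opiate use per kilogram of bodyweight per hour. That rescales the outcome and is not covariate adjustment.

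**The concern.** Neither the design nor the analysis deals with chance imbalance in characteristics that the trial already collects. If any of them predicts pain or opiate need, the crude comparison leaves explainable variation in the error term. The protocol itself indexes opiate use to bodyweight, so it treats body size as relevant to at least that endpoint.

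At stake are a somewhat wider confidence interval than necessary, and the credibility of any adjustment added later. If the arms turn out unbalanced, an adjusted analysis chosen after seeing the imbalance carries little weight.

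**Working it through.** **Inputs.** Section 10.2 has the proportion with any score above 3 falling "within the first four hours from currently 65% to 35" per cent. Section 10.3 states "A two group test with a 0.05 two-sided significance level will have 90% power to detect a redistribution" "when the sample size in each group is 63", and then: "Assuming a 10% dropout rate, 140 subjects will be recruited and randomized". The prognostic strength of the covariates is not in the documents. It is assumed below as R², the share of outcome variance explained.

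**1. The plan's own figure.** Without continuity correction:

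n = [1.96·√(2·0.5·0.5) + 1.2816·√(0.65·0.35 + 0.35·0.65)]² / 0.30² = (1.3859 + 0.8645)² / 0.09 = 56.3, so 57.

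With continuity correction: (56.27/4)·[1 + √(1 + 4/(56.27·0.30))]² = 62.8, so 63. Then 63/0.9 = 70 per arm, 140 in total. The stated figures reproduce.

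Power of the uncorrected χ² test at 63 per arm: z = (0.30·√63 − 1.96·√0.5)/√0.455 = (2.3812 − 1.3859)/0.6745 = 1.476, which gives 93.0%. A continuity-corrected test had about 91 to 92% in simulation.

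**2. Chance imbalance at 70 per arm.** The standardised difference in one continuous covariate has SD √(2/70) = 0.169.
- P(difference above 0.2 SD) = 2·[1 − Φ(1.183)] = 0.237. For at least one of four independent covariates: 1 − 0.763⁴ = 0.66.
- P(difference above 0.3 SD) = 2·[1 − Φ(1.775)] = 0.076. For at least one of four: 1 − 0.924⁴ = 0.27.

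**3. Large-sample guide.** Effective n per arm = 63/(1 − R²).

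| R² (assumed) | Effective n | Power, 65% vs 35% | Power, 65% vs 45% (assumed) |
|---|---|---|---|
| 0 | 63.0 | 93.0% | 61.9% |
| 0.05 | 66.3 | 94.2% | 64.2% |
| 0.10 | 70.0 | 95.2% | 66.5% |
| 0.20 | 78.8 | 97.1% | 71.7% |

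This ignores the cost of estimating the covariate effects, so it is optimistic.

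**4. Simulation without small-sample correction.** 63 per arm, four covariates, logistic model with standardised risk difference and influence-function standard error, 4,000 runs per cell. Entries are crude → adjusted.

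| R² | Power, 65% vs 35% | Power, 65% vs 45% | Type I error, 65% in both arms | Variance ratio, adjusted/crude (65% vs 35%) |
|---|---|---|---|---|
| 0 | 93.6 → 92.8% | 64.4 → 62.6% | 4.8 → 5.3% | 1.01 |
| about 0.05 | 93.5 → 94.2% | 64.2 → 64.8% | 5.3 → 5.8% | 0.97 |
| about 0.10 | 93.7 → 95.3% | 64.0 → 67.4% | 5.1 → 5.9% | 0.93 |
| about 0.17 | 93.4 → 96.2% | 63.1 → 70.5% | 4.3 → 5.5% | 0.88 |

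The adjusted test rejects slightly too often under the null, so part of its apparent gain is not real. In a further 3,000 runs per setting with four or five covariate terms, its type I error was 5.3 to 7.3%, against 4.2 to 5.8% for the crude test.

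**5. With a small-sample correction.** In those 3,000-run settings the change in power was about 0 to +2.5 points at the planned effect and about −1 to +6.5 points at a 20-point difference. Non-prognostic covariates cost about 0.5 to 2 points. The Monte Carlo standard error of one power estimate is √(0.93·0.07/3000) = 0.5 point near 93%, and √(0.64·0.36/3000) = 0.9 point near 64%.

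The ends of these ranges depend on the correction chosen. A separate set of 4,000 runs, with a correction that brought type I error to 4.7 to 5.3%, gave at the planned effect 94.2 → 95.3% (R² about 0.10) and 93.2 → 96.0% (about 0.17). At a 20-point difference it gave 65.2 → 62.7%, 64.3 → 64.8% and 64.0 → 67.0% for R² of about 0.05, 0.10 and 0.17.

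**The case against.** The strongest reply is that nothing in the plan is wrong. After 1:1 randomisation a crude χ² test is valid, it matches the method used to size the trial, and the imbalances in step 2 are already counted in its 5% error rate. A reader might infer from the unstratified design that the primary result will be biased or its error rate inflated. The documents do not support that: chance imbalance averages out over randomisations and is not bias. This part of the reply stands in full.

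A reader might also infer that adjustment is free precision. That does not hold either. No section says how strongly sex, age, BMI or ASA class predict a score above 3, and no baseline pain score is listed. Non-prognostic covariates lose power, and an uncorrected standard error is mildly anti-conservative at this size. Nor do the figures show that an adjusted model must replace the χ² test as the primary analysis.

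What remains against the reply is narrow. The data are collected anyway, the variance of the estimate fell by about 7 to 12% in the settings with R² of about 0.10 to 0.17 at the planned effect, and adjustment is credible only if fixed in advance.

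**Conclusion.** The point holds as a low-priority improvement. Every comparison in section 10.5 is unadjusted and randomisation is unstratified, while four usable baseline variables are recorded before surgery. The χ² test is valid.

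Under an assumed R² of about 0.05 to 0.17, adjustment with a small-sample correction changes power by about 0 to 2.5 points at 65% versus 35%, and by about −1 to +6.5 points if the true difference is 20 points. If the covariates are not prognostic, it costs about 0.5 to 2 points. These ends are approximate: the separate corrected runs reached +2.8 points at the planned effect, and ran from −2.5 to +3.0 points at 20 points.

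The size rests on three assumptions: the R² range, covariates that act additively on the log-odds, and 63 analysed patients per arm. For pain averages and opiate use the gain cannot be sized, because the documents give no standard deviations or correlations.

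**What to change.** Before unblinding, add to section 10.5:

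- **Covariates.** A short fixed list, for example sex, age and BMI (the latter two as continuous terms), with ASA class as one term at most.
- **Primary endpoint.** A covariate-adjusted standardised risk difference with 95% confidence interval and a named small-sample correction to its standard error, reported beside the χ² test. The χ² test may stay as the primary test. Naming the risk difference matters because an adjusted odds ratio is a conditional measure and answers a different question. State that the unadjusted result is used if the model cannot be fitted.
- **Average maximal pain and total opiate use.** Linear regression with the same covariates. For ward opiates, name a transformation that allows zero values, since a plain logarithm does not.

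The cost is a few sentences, handled as an amendment under section 10.7, and slightly more analysis work. The downside is a small loss of power in the adjusted analysis if the covariates prove non-prognostic.

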4.3 Other objectives of interest

Other objectives of interest are as follows:

- Monitoring of PONV and its distribution between the groups.
- Comparing time to first defecation after completion of surgery in both groups in regard of a beneficial effect in the “lidocaine group”.
- Comparing length of hospitalization of both groups in regard of a beneficial effect in the “lidocaine group”.

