5.3 Other outcomes of interest

- any event of postoperative nausea and vomiting (subdivided by event of no nausea (PONV = 0), event of nausea without vomiting (PONV = 1) and event of nausea with vomiting (PONV = 2)) during first 48 hours after completion of surgery
- time to first defecation (quantified in hours)
- duration of hospitalization (quantified in days)

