POD 1	ABTEILUNG	VAS Monitoring 6am, 2pm, 10pm Studiensite 10am, 2pm	- Erinnerung des Pat. durch Pflege- Studienpersonal - Prim./Sek. Variablen im CRF erfassen - AE, SAE, ADR erfassen
POD 2	ABTEILUNG	VAS Monitoring 6am, 2pm Studiensite 10am, 2pm (Safety follow-up)	- Erinnerung des Pat. durch Pflege- Studienpersonal - Prim./Sek. Variablen im CRF erfassen - AE, SAE, ADR erfassen
POD X	Studien- koordination	Safety follow-up	- telefonisch / ambulant - AE, SAE, ADR erfassen

table 2: study sequence describing process and daily course, POD X will be postoperative day seven or day of patients discharge

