9.2 Assessments of outcomes

Assessment of Pain

Pain will be assessed by the visual analogue scale (VAS) or the numeric rating scale (NRS), respectively, 0 indicating no pain and 10 maximal possible pain sensation. VAS/NRS scoring systems are validated and frequently used methods to evaluate variations in pain intensity. The VAS/NRS score will be recorded by trained nurse practitioners in the PACU, respectively on the surgical ward, once per hour during the first four hours after completion of surgery. Analysis of the primary outcome (any development of

VAS/NRS score > 3, in hourly measurements within the first four hours after completion of surgery) will be dichotomized accordingly. Thereafter, VAS/NRS score will be assessed by a patient questionnaire for self-evaluation and in addition by trained nurse practitioners during their daily round (10am and 2pm respectively +/- 30 minutes) during the first 48 hours after completion of surgery. Missing postoperative VAS/NRS scores, required for primary and secondary endpoints, will be handled as interpolation values, calculating an average score between last recorded scores before and after the missing value.

Secondary endpoints

- Average maximal pain intensity during first four hours and during 48 hours
- total amount of opiates as documented in the electronic anesthesia records during surgery and on PACU
- total amount of opiates applied on surgical ward, recorded in the charts. Values will be categorized in total amount in mg, average amount in mg/h and indexed amount in mg/kg bodyweight/h
- any event of postoperative nausea and vomiting (subdivided by event of no nausea (PONV = 0), event of nausea without vomiting (PONV = 1) and event of nausea with vomiting (PONV = 2)) during first 48 hours after completion of surgery
- time to first defecation after completion of surgery (quantified in hours)
- total time spent in hospital after completion of surgery (quantified in days)

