9.4 Procedures at each visit

Each patient will be visited after surgical treatment and transfer to PACU/ICU by a study nurse or the Study Investigator. The VAS/NRS score (registration of any development of VAS/NRS score > 3) will be assessed by trained nurse practitioners in the PACU/ICU in hourly measurements during the first four hours after completion of surgery, respectively until discharge to the surgical ward. Thereafter, VAS/NRS score will be assessed by a patient questionnaire for self-evaluation and in addition by trained nurse practitioners during their daily round (10am and 2pm respectively ± 30 minutes) during the first four hours and during 48 hours after completion of surgery. VAS/NRS scores and vital parameters will be recorded. Incidental questions about upcoming study process will be answered. Infusion of the investigational product will be stopped four hours after the end of surgery (or before the transfer of the patient from the PACU to the surgical ward, whichever occurs first). Pain evaluation will take place every eight hours by recording the maximum VAS/NRS score experienced within this period. Recording of VAS/NRS scores will be stopped at 2pm respectively ± 30 minutes on second postoperative day. Completion of study investigation will be finalized by collecting the study documents at study nurses final visit on second postoperative day at 2pm respectively ± 30 minutes.

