10.8 Handling of missing data and drop-outs

Missing postoperative VAS/NRS scores, required for primary and secondary endpoints, will be handled as interpolation values, calculating an average score between last recorded scores before and after the missing value. Missing data for secondary endpoint PONV or time to first defecation will be handled as no occurrence of PONV (PONV 0) or no defecation yet. In case of drop-out, data collected till patients drop out will be neglected and not taken into account of statistical consideration of the study.

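### Time to first defecation is cut off at 2pm on postoperative day 2, but section 10.5 names no method that can handle patients who have not yet had the event

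*Combined protocol and SAP*

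**What the plan says.** Section 4.3 sets the aim: "Comparing time to first defecation after completion of surgery in both groups", looking for a benefit of lidocaine. Section 5.3 defines the outcome as "time to first defecation (quantified in hours"), and section 9.2 lists it among the secondary endpoints.

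Observation is short. Section 6.1 ends it at the study nurse's "final visit on second postoperative day 2pm respectively +/- 30 minutes". Section 9.4 agrees: "Completion of study investigation will be finalized by collecting the study documents at study nurses final visit on second postoperative day at 2pm". In the study-sequence table of section 8.1, secondary variables are recorded up to POD 2. The later contact, POD X, lists only safety items: "telefonisch / ambulant - AE, SAE, ADR erfassen".

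Section 10.5 gives χ² for dichotomous data. For the rest: "Continuous data will be analyzed by parametric or non-parametric test for unpaired comparison as appropriate". No Kaplan-Meier, log-rank or Cox analysis and no censoring rule appears anywhere. Section 10.8 says that missing data on this endpoint are handled as "or no defecation yet".

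**The concern.** A patient who has not defecated by 2pm on day 2 contributes a lower bound, not a time. An unpaired test of continuous values cannot use a lower bound as it stands. Someone must drop the patient, enter the cut-off as if it were the observed time, or assign the worst rank. The plan does not choose, so the choice can be made after the data are seen, and the three routes can give very different answers.

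There is a second fault in section 10.8. A patient whose defecation was simply not recorded is given the same status as one known not to have defecated. The first has unknown status after the last contact, and the second is a genuine non-event up to the cut-off.

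At stake are the size of any bowel-recovery benefit in hours and the chance of detecting it. Faster return of bowel function is part of the rationale in sections 3.1 and 3.2.

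**Working it through.** **Inputs from the documents.** End of observation at 2pm on day 2 (6.1, 9.4); 63 per arm and two-sided 0.05 (10.3). The plan gives no figure for this endpoint to reproduce: no expected times, no expected share without an event, and no power.

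**Length of observation.** If surgery ends at clock hour h, follow-up is 48 + 14 − h hours. For assumed end times of 10:00 and 17:00 this is 52 h and 45 h. The cut-off is therefore nearly common to all patients, and 48 h is used below.

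**Assumptions, none from the documents.** Weibull times with shape k of 1, 1.5 or 2; medians of 60 h (placebo) and 40 h (lidocaine).

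**Share without an event at 48 h**, 2^−(48/median)^k:
- placebo: k = 1, 2^−0.80 = 57%; k = 2, 2^−0.64 = 64%
- lidocaine: k = 1, 2^−1.20 = 44%; k = 2, 2^−1.44 = 37%

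**True mean difference**, (60 − 40) × Γ(1 + 1/k)/(ln 2)^(1/k):
- k = 1: 20/0.693 = 28.9 h
- k = 2: 20 × 0.886/0.833 = 21.3 h

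**Difference seen under each way of entering non-events.**
- Dropped: 1 to 2 h (simulation).
- Cut-off entered as the value: for k = 1 each mean is (median/0.693) × (1 − share without event), so 86.6 × 0.426 = 36.9 h and 57.7 × 0.565 = 32.6 h, a difference of about 4.3 h. Across the shapes it is about 4 to 6 h.

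**Simulated power, 63 per arm, over the three shapes.**

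| Handling of non-events | Power |
|---|---|
| Dropped, t-test | 6-9% |
| Cut-off as the value, t-test | 31-77% |
| Tied at the last rank, rank test | 35-87% |
| Censored, log-rank | 37-88% |

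Repeat runs move these figures by a point or two.

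**Sensitivity to the medians.** With 30 v 20 h, the cut-off t-test and the rank test come within about 6 points of log-rank. At shape 2 only 17% and 2% are censored: the t-test with non-events dropped has about 78% power, the cut-off and rank versions 97-98%, and log-rank 99%.

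**A second set of assumptions.** Shape 2, event-rate ratio 1.6, surgery ending between 10:00 and 17:00. For control medians of 30, 40, 48, 60 and 72 h, log-rank power is 70, 59, 52, 42 and 34%. A rank test with non-events dropped has 30, 13, 8, 5 and 4%; with non-events last, 61, 55, 49, 41 and 33%. At a control median of 48 h, a true difference of 10.7 h in favour of lidocaine becomes 1.5 h if non-events are dropped and 4.1 h if the cut-off is the value.

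**Type I error.** With no true effect, every method rejected in about 5% of runs.

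**Can a median be reported?** With 63 patients followed to 48 h, the Kaplan-Meier median needs at least 32 events. At a true control median of 60 h the event probability is 1 − 0.574 = 0.426 (k = 1) or 1 − 0.642 = 0.358 (k = 2). The binomial probability of 31 or fewer events is then 88% or 99%, so the control median would usually not be reached.

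**The case against.** A reader might infer that the plan throws away patients without an event and so would hide a large bowel effect. The documents do not support that. No section says to drop them: section 10.8 keeps such a patient with a status and removes only drop-outs, and section 10.5 permits a non-parametric test. A natural combined reading is a rank test with non-events last, and because the cut-off is nearly common, that test loses only a few points of power against log-rank. The 6-9% figure belongs to one unfavourable reading under assumed medians.

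Entering the cut-off is not always wrong either. If everyone is followed to one fixed horizon, the mean of the capped times is the restricted mean, a legitimate quantity when labelled as such. It misleads only when reported as the difference in time to defecation.

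Two further inferences also fail. Nothing here raises the false-positive rate. Nor does it touch the trial's main conclusion: the hypothesis (10.2) and sample size (10.3) concern pain only, and sections 4.3 and 5.3 class defecation among other objectives and outcomes, although the synopsis and section 9.2 call it secondary.

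What stands is that the documents do not specify the rank approach, leave a parametric test open, and treat an unrecorded time as a known non-event. A rank test would also give no estimate in hours.

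**Conclusion.** The concern holds as a mismatch between endpoint and method, not as proof of a lost effect. The plan foresees right-censored times, names only tests that cannot take them as they stand, and codes missing records as non-events. Depending on the analyst's choice, the difference in hours is understated and power falls by anything from a few points to nearly all of it. The figures are illustrative: they rest on assumed Weibull times and medians, because the documents give no defecation data. If most patients defecate before 2pm on day 2, the cut-off and rank approaches lose little. The change should be made because it removes a post-hoc choice at no cost. It concerns a secondary or other outcome only.

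**What to change.** - **Section 10.5:** analyse time to first defecation with Kaplan-Meier curves and a log-rank test. Report a hazard ratio, or the difference in restricted mean time to a stated common cut-off within the day-2 observation period, with a 95% CI. Give medians only if they are reached.
- **Section 10.8:** for this endpoint, replace the rule for missing records with censoring at the last time the patient's status was known. Keep known non-events at the final visit distinct from unrecorded times.

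**Cost:** a sentence or two in each section, by the amendment route of section 10.7 and before unblinding. No more patients are needed, and SPSS, the planned software, can run the analysis.

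**Optional, and not part of the core fix:** ask about defecation at the POD X contact. This adds a data item, since that contact now lists safety events only. Under section 11.8 it falls on day seven or at discharge, whichever is earlier, so follow-up would vary between patients, could be linked to recovery, and could still leave some times censored.
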